1.1 Background

Leber's Hereditary Optic Neuropathy

LHON is a maternally inherited loss of vision due to atrophy of the optic nerve. More than 90% of individuals with LHON harbour one of three point mutations in mitochondrial DNA (mtDNA) (G11778A, T14484C, G3460A) affecting genes encoding complex I subunits of the respiratory chain (Mackey 1996, Newman 2013). It typically presents in young adults, mostly men, as painless acute or subacute visual failure of both eyes in quick succession. The estimated prevalence is approximately 2.2 per 100,000 (Mascialino et al., 2012) and LHON is thus an Orphan Disease according to EU and US criteria. Clinically, the acute phase of the disease begins with blurring of central vision and colour de-saturation that affect both eyes. After the initial symptoms, both eyes are usually affected within two to four months from disease onset. Within 12 months of visual loss in one eye, over 97% of patients will have second eye involvement. The central visual acuity deteriorates to the level of counting fingers in up to 80% of cases. Following the nadir, acuity may improve. The degree of improvement is dependent, in part, also on the precise genetic mutation of affected patients. With disease progression, individuals then proceed into the atrophic phase and are usually legally blind for the rest of their lives with a permanent large centrocecal scotoma (Sadun et al., 2011).

Idebenone 2-(10-hydroxydecyl)-5,6-dimethoxy-3-methyl-cyclohexa-2,5-diene-1,4-dione has been suggested to be effective in by-passing the complex I deficiency resulting from the mtDNA point mutations and maintaining cellular energy production by stimulating the alternative pathway through complexes II and III (Haefeli et al., 2011). This activity may also reduce the production of reactive oxygen species (ROS) associated with complex I deficiency and to protect cell membranes and mitochondria from oxidative damage. This provides a strong rationale for its use in LHON (summarized in Gueven and Faldu, 2013; Gueven, 2014).

Detailed information on the medicinal product and on non-clinical data is available in the Investigator's Brochure (IB).

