6.1 Outline of Study Procedures

All study procedures are outlined in the Schedule of Assessments shown below. A more detailed description of the study procedures performed at each visit is given in the following sections of the protocol.

Patients will be enrolled to receive 900 mg idebenone (2 tablets 3 times daily with meals) for 24 months. Starting with Baseline/Visit 1 sufficient study medication will be dispensed to last until the next visit. The patient will take the first dose of study medication on Day 1, the day of the Baseline Visit (or as instructed by the site investigator / study nurse).

The duration of study participation for each individual patient will be approximately 25 months and comprise 9 study visits (V1-V9). Before any study-specific procedures are undertaken, the patient (and parent/legal guardian if required) will have been thoroughly informed by the investigator of the purpose of the study, the relevant procedures and of patient rights and responsibilities. Patient information will be distributed in writing and signatures of consent obtained on the consent form. (See also Section 10.3).

Patient enrolled in the study will receive study medication at Baseline/Visit 1; the first study medication intake is on the day of the Baseline/Visit 1 (or as instructed by the site investigator / study nurse). During the 24 month treatment period, visits take place at Month 1, Month 3, Month 6, Month 9, Month 12, Month 18 and Month 24. Visit 8 (Month 24) is the endpoint of treatment. Visit 9 is a follow-up, 28-35 days after study medication discontinuation.

Physical examination and measurement of vital signs will be undertaken at Baseline/Visit 1 and then at Visit 4/Month 6, Visit 6/Month 12, Visit 7/Month 18 and Visit 8/Month 24.

Safety blood and urine and safety assessments will be done at each visit.

A urine or serum pregnancy test will be performed for WCBP at the baseline visit and further when clinically indicated.

Assessment of VA (assessed by ETDRS charts and reported in logMAR value) will be done at every visit.

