6.5 Discontinuation / Withdrawal

6.5.1 Conditions for discontinuation/withdrawal

Reasons that a patient may be withdrawn from the study include the following:

- adverse event(s)
- major protocol deviation/violation (e.g. Intake of any prohibited concomitant medication as listed in Section 6.3)
- inclusion criteria not met/exclusion criteria met
- genetic diagnosis reveals that a patient does not harbour a LHON-specific mtDNA mutation
- pregnancy
- lack of compliance with study medication
- patient withdrew consent
- lost to follow-up
- death
- other (reason to be documented)

Each patient has the right to withdraw from the trial at any time for any reason without affecting the right to treatment by the investigator. The investigator also has the right to withdraw the patient if he/she judges it in the patient's best medical interest. In either case, all attempts should be made to document the reason for withdrawal. Santhera Pharmaceuticals (Switzerland) Ltd reserves the right to request the withdrawal of a patient due to protocol deviation, administrative or other reasons.

It is understood by all concerned that an excessive rate of withdrawals can render the study non interpretable, therefore every effort should be made to avoid unnecessary withdrawals. However, WHENEVER a patient is withdrawn from a trial, FOR WHATEVER REASON, a final study evaluation must be completed for that patient, including all Visit 9 evaluations if possible, and stating the reasons why the patient was withdrawn. All documentation concerning the patient must be as complete as possible. Withdrawals due to non-attendance must be followed-up by the investigator to obtain the reason for non-attendance.

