12.4 Sensitivity analysis due COVID-19 pandemic

Due to the COVID-19 pandemic, study visits can be rescheduled within

- Visits 6 and 7 it is 90 days,
- Visit 9 it is 60 days.
- Visit 8 if

SNT-IV-005 Statistical Analysis Plan

Confidential

Study: SNT-IV-005

- ≤ 60 days later than planned visit per protocol and ≤30 days no study medication intake at rescheduled visit 8 then visit 8 was performed
- >60 days later than planned visit per protocol and >30 days no study medication intake at rescheduled visit 8 then visit 9 was performed and visit 8 was skipped

of originally scheduled visit date.

The impact of the rescheduling or visits missed due to COVID-19 will be investigated with a sensitivity analysis using the approach proposed by Meyer et al (2020).

At the time of 12 months follow-up (Visit 6) only one patient missed the visit due to COVID-19 pandemic. Therefore, sensitivity analysis will be used in mITT population on the 24 months data (Visit 8).

Post-treatment data (Visit 9) will not be imputed.

All missing data will be categorized as being missing due to COVID-19 or due to other causes. In the first step, the missing data due to COVID-19 will be imputed using the assumption of MAR. In the second step, the remaining missing data will be imputed using the assumption of MNAR. For observations MNAR, last-observation-carried-forward will be applied, using only data collected from month 12 visit (Visit 6) onwards. For patients with no data in this time frame, the data from the follow-up visit will be used as the 24 month assessment. This sensitivity analysis will be repeated for a dataset where the Visual Acuity assessments that were delayed by more than 30 days from the scheduled visit date will be set as missing and included in the category of missed assessments due to COVID-19.

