For the missing data assuming MAR, the multiple imputation approach will be applied. The imputation will consider and use only LEROS data, since the matched external natural history control group is not longitudinal data and does not include any missing data. As the disease does not progress linearly, only the 12 month (Visit 6) and 18 month (Visit 7) data will be used for the imputations. First the MCMC methodology will be used to impute the data to obtain monotonously missing data. Then imputation will be completed using regression imputation for the monotonously missing data. Analysis model will be run for the imputed data by imputation and SAS procedure *mianalyze* will be used to calculate the combined results.

SAS code to perform multiple imputation on missing visual acuity results assuming MAR:

/* STEP 1: LEROS data imputation*/

/*impute non-monotonously missing observations */

proc mi data=visual acuity out=visual acuite monotone nimpute=1000 seed=xxx;

var logMAR_v6 logMAR_v7 logMAR_v8;

```
mcmc chain=multiple impute=monotone;
run;
/*use regression imputation to complete MAR imputation*/
proc mi data= visual_acuite_monotone out=visual_acuite_impute=1 seed=xxx;
  var logMAR_v6 logMAR_v7 logMAR_v8;
  monotone regression;
run;
    STEP 2: calculation of visit 8 CRB from baseline for imputed values
             visit 8 CRB from baseline should be calculated with the same SAS code
             used for the main analysis of the primary endpoint but use visit 8 as main variable
             input dataset: visual acuite imputed;
             calculate LEROS visit 8 CRB;
             output dataset: leros crb imputed
*/
    STEP 3: repeat 1000 times Natural History data used the main analysis of the
             primary endpoint and join with LEROS data set which has the imputed CRB calculation*/
data natural history repeated;
  set natural history analysis data;
    do Imputation = 1 to 1000;
       output;
    end;
  run;
data all data joined;
        set leros crb imputed natural history repeated;
run;
    STEP 4: applying logistic model over the new imputed CRB data*/
proc sort data= all_data joined; by Imputation; run;
proc logistic;
   by _Imputation_;
```

```
class treatment gender mutation / param=ref;
   model CRB(event='1') = treatment gender mutation / link=logit clodds=pl;
   ods output ParameterEstimates = ParameterEstimates;
   ods output CLOddsPL = CLOddsPL;
run;
     STEP 5: calculate the logistic analysis combined results*/

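### In the Month 24 COVID-19 sensitivity analysis, a follow-up visit held long before Month 24 can stand in as the 24-month value for patients who left before Month 12

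*SAP*

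**What the plan says.** SAP 12.4 describes a sensitivity analysis of the Month 24 (Visit 8) data in the mITT population. Values missing because of COVID-19 are multiply imputed under MAR. For the rest: "In the second step, the remaining missing data will be imputed using the assumption of MNAR". The method for that step is that "last-observation-carried-forward will be applied, using only data collected from month 12 visit (Visit 6) onwards". A fallback follows: "For patients with no data in this time frame, the data from the follow-up visit will be used as the 24 month assessment". No date limit is attached to it.

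Four other places determine what the fallback does.

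- Protocol 6.1 fixes the follow-up visit relative to stopping drug, not to Month 24: "Visit 9 is a follow-up, 28-35 days after study medication discontinuation".
- Protocol 6.5.1 says that, whenever and for whatever reason a patient is withdrawn, "a final study evaluation must be completed for that patient, including all Visit 9 evaluations if possible".
- SAP 8.3 admits a patient to mITT with one dose, one of the three major mutations and a single post-baseline acuity, so early leavers are included.
- SAP 16 defines stabilisation as acuity better than 1.0 logMAR at baseline and still better than 1.0. Stabilisation alone makes an eye a responder (CRB).

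**The concern.** The plan limits carry-forward to Visit 6 onwards and then sets that limit aside for exactly the patients who have nothing from Visit 6 onwards. What replaces it is a single value, normally off drug, that can precede Month 24 by almost two years.

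The timing matters in this disease. Protocol 1.1 says that "The central visual acuity deteriorates to the level of counting fingers in up to 80% of cases" and that both eyes are usually affected within two to four months of onset. An eye seen before its decline can be scored as having kept its vision for two years. The MAR step of the same section restricts its own predictors for a related reason: "As the disease does not progress linearly, only the 12 month (Visit 6) and 18 month (Visit 7) data will be used".

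The two sides are also treated differently. A Month 24 control eye enters only with an actual assessment at the matched time (SAP 8.5.1, repeated for 24 months), and SAP 12.4 says that the matched controls contain no missing data. At stake is whether this analysis gives an interpretable Month 24 comparison.

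**Working it through.** **1. Timing.** Visit 9 falls about one month after drug is stopped. Stopping at Month 1 puts it at about Month 2, which is 24 − 2 = 22 months before the time it is taken to represent. Across leavers before Month 12, the value can date from about Month 1 to Month 12.

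**2. The plan's own figure.** Protocol 9.6 and SAP 6 give 110 evaluable LEROS eyes for 90% power, at 22% versus 40%. With 175 control eyes, pooled variance, two-sided 0.05 and eyes treated as independent, I get 111 eyes; 110 eyes give 89.9% power. Drop-out of 30% gives 110 / 0.70 = 157.1, so 158 eyes or 79 patients, consistent with the planned 80 patients (160 eyes). These figures are not in dispute; they supply the denominators below.

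**3. Stabilisation component.** The excess in the Month 24 responder proportion is

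excess = f × b × (qe − q24)

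- f: share of LEROS eyes with no value at Visits 6 to 8 and an early Visit 9
- b: share of those eyes with baseline acuity better than 1.0
- qe: share of these still better than 1.0 at the early visit
- q24: share of these truly better than 1.0 at Month 24

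The documents give none of the four, so all are assumptions. The upper end for f, 30%, is the whole planned drop-out.

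| Case | f | b | qe | q24 | Excess |
|---|---|---|---|---|---|
| Low | 0.05 | 0.10 | 0.7 | 0.5 | 0.1 point |
| Mid | 0.10 | 0.25 | 0.9 | 0.3 | 1.5 points |
| Extreme | 0.30 | 0.40 | 1.0 | 0.2 | 9.6 points |

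Mid case in eyes: 160 × 0.10 × 0.25 = 4 eyes, and 4 × (0.9 − 0.3) = 2.4 responders too many.

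**4. What that would do alone.** Take no true difference and 22% in both groups. This is the Month 12 planning rate, used as a placeholder because no Month 24 rate is given. With 160 versus 175 independent eyes, the mid case gives 23.5% versus 22%, an apparent odds ratio of 1.09. The chance of a significant result favouring treatment rises from 2.5% to 5.1%. The low case gives 1.01 and 2.6%; the extreme case gives 1.64 and 51%.

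**5. The opposing component.** The other eyes contribute f × (1 − b) × (re − r24), where re and r24 are the shares recovered at the early visit and truly at Month 24. If recovery comes later, this is negative. For scale only, the Protocol 1.2 table of expanded-access eyes shows recovery from nadir in 24.2% at 6 months and 39.9% at last observation, a gap of 15.7 points. The patient sets differ and the patients were on treatment. Putting that gap into the mid case: 0.10 × 0.75 × (−0.157) = −1.2 points, against +1.5, which leaves about +0.3. The mid case nets to zero when the gap reaches 0.15 / 0.75 = 20 points.

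**The case against.** **Direction.** A reader might infer that the rule biases LEROS upward. The documents do not support that. Eyes already off-chart at exit, or not yet recovered, are carried as failures, and step 5 shows that this can offset much or all of the gain. The observed-case analysis omits these eyes, so adding them raises the LEROS rate only if their carried rate exceeds that of the observed eyes. As an assumed illustration, 112 observed eyes at 40% and 48 carried at 20% give (44.8 + 9.6) / 160 = 34%, a fall. This objection stands.

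**Purpose and rationale.** A reader might also infer that the analysis is meant to challenge MAR, or that carry-forward starts at Visit 6 because earlier values do not predict later ones. SAP 12.4 states its purpose as assessing the effect of rescheduled and missed COVID-19 visits. It gives the non-linearity reason only for the MAR step, and none for the carry-forward limit. Both inferences go too far.

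**Size.** It is tempting to apply the rule to all 48 planned drop-out eyes (30% of 160). That overstates it: an affected eye must be missing for non-COVID reasons, be in mITT, have no value at Visits 6 to 8 and have a Visit 9, which is obtained only if possible. The stabilisation error also needs baseline acuity better than 1.0. The Protocol synopsis plans 61 of 80 patients with Month 12 data, which leaves 19 patients, or 38 eyes, without.

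**Intended use.** The sentence might be meant for patients whose Visit 8 was skipped under the COVID-19 rules and replaced by Visit 9. But values missing because of COVID-19 go to the MAR step, not this one. A patient who missed Visits 6 to 8 but attended a late Visit 9 is a harmless case, yet the wording is not confined to it.

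**Conclusion.** The point holds as a timing defect. The rule places a value from as early as about Month 1 into the Month 24 analysis, contrary to the section's own limit to Visit 6 onwards, and nothing elsewhere in the documents corrects it. A carried early value also applies no penalty for being missing, so the MNAR label should not be read as meaning conservative.

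The stabilisation component can be inflated by about 0.1 to 9.6 points, mid case 1.5. All inputs to that range are assumed, and eyes are treated as independent. The net effect over all eyes is of unknown sign. It could be negligible if few patients leave early with baseline acuity better than 1.0.

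The reach is narrow: one Month 24 sensitivity analysis. The Month 12 primary analysis and its own multiple imputation do not use the rule, and no stated success criterion depends on it. This is a minor point, worth correcting because the correction is so small.

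**What to change.** Replace the fallback sentence in SAP 12.4 with three rules:

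1. A Visit 9 value is used as the Month 24 assessment only if it falls within 24±3 months of baseline, the window applied to the controls.
2. Carry-forward of values from Visit 6 onwards stays as planned. The text should say whether a Visit 9 held after Month 12 but before that window counts as such a value; at present it does not.
3. Remaining eyes with no acuity from Month 12 on are counted as non-responders (CRB = 0) in this sensitivity analysis. This also covers early leavers with no Visit 9, for whom the SAP gives no rule in this step.

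The SAP should say that rule 3 is conservative. In the mid case it removes 4 × 0.9 = 3.6 carried successes (3.6 / 160 = 2.25 points), of which only 2.4 are false, so some eyes that truly kept their vision are scored as failures. The cost is a short text edit and a sensitivity estimate that may become slightly less favourable. No new data are needed.

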8.5 LEROS and NH matched datasets

In order to optimize the comparability of patient data in the NH control set and the LEROS ITT population, subsets from the NH control set will be prospectively defined. These subsets will be matched separately for all the efficacy analyses using the matching rules defined in section 8.5.1 and 8.5.2.

A total of 8 datasets (as exemplified in Table 8-1) will be generated based on the matching algorithm (taking in consideration time since symptoms onset at BL and follow-up in analysis).

Table 8-1- LEROS and NH matched datasets

time since symptoms onset	follow-up (months)				
≤1 year	6	12	18	24	
> 1 year	6	12	18	24	

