The described process will be repeated for the secondary analyses applied for the 6, 18 and 24 month time points for the eyes with $BL \le 1$ year after the onset of symptoms.

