12.1 Primary endpoint

Endpoint: Proportion of eyes with clinically relevant recovery (CRR) of visual acuity from Baseline (BL) or in which BL VA better than 1.0 logMAR was maintained at Month 12 in patients treated with Raxone® ≤1 year after the onset of symptoms, compared to matching external natural history control group. CRR definition is presented in section 16.

Analysis sets: Primary endpoint analysis will use all LEROS mITT eyes that are ≤1 year since onset of symptoms at BL and have the Month 12 assessment. External NH control set is generated as described in section 8.5.1 (Matching algorithm for the primary endpoint), using VA assessments within 12±3 months from BL.

Analysis method: The primary endpoint will be analysed using a logistic regression model. The binary response will be used as the dependent variable. The independent variables include the treatment group (Raxone® treated patients versus untreated control group), gender (male, female) and mutation group (G11778A, G3460A, T14484C) as fixed factors.

The difference between the Raxone® treated patients versus NH group will be estimated with odds ratio, two-sided 95% confidence intervals and two-sided p-values

```
proc logistic;
  class treatment gender mutation / param=ref;
  model CRB(event='1') = treatment mutation gender / link=logit clodds=pl;
  oddsratio treatment;
run;
```

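### In SAP 12.4 the STEP 3 comment points the Month 24 COVID-19 sensitivity analysis at the Month 12 natural-history controls, in conflict with the 24-month matched set planned in SAP 8.5.

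*SAP*

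**What the plan says.** **LEROS arm.** SAP 12.4 notes that only one patient missed Visit 6 because of the pandemic and therefore places the sensitivity analysis at Month 24 in the mITT population. STEP 2 of the SAS block was adapted to this: CRB is to be derived with the code "used for the main analysis of the primary endpoint but use visit 8 as main variable".

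**Control arm.** STEP 3 tells the programmer to "repeat 1000 times Natural History data used the main analysis of the" (the comment continues on the next line) "primary endpoint and join with LEROS data set which has the imputed CRB calculation". The same comment stands in the Month 12 imputation code in SAP 12.1.1, where it is correct. The line of code beneath it reads in a generic natural-history analysis dataset with no time point in its name.

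**What the primary-endpoint controls are.** SAP 12.1 builds them by the algorithm in 8.5.1 for eyes ≤1 year from onset, "using VA assessments within 12±3 months from BL".

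**What is planned for Month 24.** SAP 8.5 says of the control subsets: "These subsets will be matched separately for all the efficacy analyses using the matching rules". It adds: "A total of 8 datasets (as exemplified in Table 8-1) will be generated based on the matching algorithm". Table 8-1 crosses two onset groups with follow-up at 6, 12, 18 and 24 months. For eyes ≤1 year from onset, 8.5.1 adds: "The described process will be repeated for the secondary analyses applied for the 6, 18 and 24 month time points". SAP 8.5.2 does the same for eyes >1 year.

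**The concern.** STEP 2 moved to Month 24 and STEP 3 did not. Taken at its word, the block sets LEROS outcomes at Visit 8 beside control outcomes at 9 to 15 months. The STEP 4 model contains treatment, gender and mutation only, so nothing adjusts for follow-up length.

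Follow-up length can matter here. Protocol 1.1 says that acuity may improve after the nadir, and SAP 12.4 itself notes that the disease does not progress linearly. CRB combines recovery, which can accumulate with time, and maintenance of good baseline acuity, which can be lost with time. An extra year could therefore move the rate either way.

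The second problem is interpretation. A sensitivity analysis for missed visits should change the handling of missing data and hold the controls fixed. Here the control set would change as well, so a shift from the main Month 24 odds ratio could not be attributed to pandemic missingness, which is what 12.4 is meant to examine. The same applies to the planned repeat in which assessments delayed by more than 30 days are set to missing.

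**Working it through.** **Step 1. Set the passages side by side.**

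| Element | 12.1.1 (Month 12) | 12.4 (Month 24) |
|---|---|---|
| LEROS outcome, STEP 2 | CRB at Visit 6 | CRB at Visit 8 (adapted) |
| Controls, STEP 3 comment | primary-endpoint set | primary-endpoint set (not adapted) |
| Control follow-up implied | 12±3 months | 12±3 months |
| Set planned in Table 8-1 | 12 months | 24 months |

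Only the STEP 3 cell under 12.4 disagrees with Table 8-1. The two control sets need not contain the same eyes or baselines: 8.5.1 keeps a baseline only if it has a follow-up value in the relevant window, so changing the window can change both.

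**Step 2. Reproduce the plan's own figure.** The point rests on no stated number. The related planning figure in SAP 6 is 90% power with 110 LEROS eyes, 40% against 22%, and 175 natural-history eyes. The check uses a two-sided 0.05 test (SAP 9) and the normal approximation with pooled variance under the null:

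- pooled rate = (110×0.40 + 175×0.22)/285 = 0.2895
- SE0 = √[0.2895×0.7105×(1/110 + 1/175)] = 0.0552
- SE1 = √[0.40×0.60/110 + 0.22×0.78/175] = 0.0562
- power = Φ[(0.18 − 1.96×0.0552)/0.0562] = 89.9%

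The figure reproduces.

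**Step 3. Illustrate the literal reading.** The documents give no Month 24 control rate, so q below is an assumed range. Suppose the drug has no effect and both arms truly have rate q at Month 24, but the controls enter at their Month 12 planning rate of 22%.

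- Apparent odds ratio = [q/(1−q)] / [0.22/0.78]. For q = 0.30: 0.4286/0.2821 = 1.52.
- The chance of a significant result favouring LEROS uses the Step 2 formula with q in place of 0.40. For q = 0.30: pooled rate 0.2509, SE0 = 0.0527, SE1 = 0.0538, and Φ[(0.08 − 1.96×0.0527)/0.0538] = 33%.
- The last column assumes LEROS at 40% and compares it with controls at q. Against the Month 12 controls it would always print 0.6667/0.2821 = 2.36.

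| Assumed q | Apparent OR, no effect | Chance of significance favouring LEROS | Like-for-like OR, LEROS 40% |
|---|---|---|---|
| 18% | 0.78 | not computed | 3.04 |
| 20% | 0.89 | not computed | 2.67 |
| 22% | 1.00 | 2.5% (nominal) | 2.36 |
| 25% | 1.18 | 9% | 2.00 |
| 30% | 1.52 | 33% | 1.56 |
| 35% | 1.91 | 67% | 1.24 |

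These rows show only that the result is sensitive to the choice of controls. They treat eyes as independent, omit gender and mutation, and use Month 12 planning counts rather than Month 24 mITT counts.

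**The case against.** The strongest reply is that the Month 12 reference sits in a comment, above a placeholder dataset name that fixes no time point. A programmer who reads 12.4 with 8.5 could supply the 24-month set, and 8.5 suggests that this was intended. SAP 12.2 also analyses the ≤1-year group at Month 24 separately for each follow-up, against a matching control group. A reader might infer that the sponsor chose mismatched controls, or that the executable code enforces them. The documents support neither: this is an uncorrected copied comment that conflicts with 8.5. What remains is that the comment is the only instruction in 12.4 on which controls to join. The prose there speaks only of the matched external control group, without a time point.

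A reader might also infer that every treated eye has 24 months of follow-up against 9 to 15 for controls. That goes too far. Under 12.4, values missing for reasons other than COVID-19 are carried forward from Visit 6 onwards, so some treated eyes would carry Month 12 or Month 18 values.

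Finally, a reader might infer a bias in favour of idebenone, or a threat to the trial's main conclusion. The direction is unknown, as the 18% and 20% rows show. The only hypothesis stated in SAP 7 is the Month 12 comparison, which does not use this block. The chance of p<0.05 also has limited meaning for a supportive analysis with no confirmatory role.

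**Conclusion.** The STEP 3 comment is wrong as written. It is an internal inconsistency, not a deliberate analysis choice. Followed literally, it makes the Month 24 COVID-19 sensitivity analysis and its delayed-visit repeat compare arms with different follow-up, and neither could be read against the main Month 24 result.

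The reach is limited to those two supportive runs. The primary analysis, its own sensitivity analyses and the main Month 24 secondary analysis stand. Neither the size nor the direction of the bias can be derived from the documents, and the illustrative figures depend wholly on the assumed Month 24 control rate. It should be corrected before the analysis is run, but it ranks below defects that touch the primary result.

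**What to change.** In SAP 12.4 STEP 3, replace the reference to the primary-endpoint controls with the Table 8-1 natural-history dataset matched for 24 months in eyes ≤1 year from onset, and give that dataset an explicit name in the code. State in the text of 12.4 which onset group or groups the analysis covers. If the >1-year group is also analysed, name its own 24-month set from Table 8-1. Apply the same correction to the repeat with delayed assessments set to missing.

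The cost is one line of code comment, a dataset name and a sentence of text. No new data or matching work is needed, because SAP 8.5 already plans these datasets.
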